## 1 Protocol Summary

### 1.1 Synopsis

**Protocol Title:**

Phase I, Open-label, Single Dose Study to Investigate the Effect of Hepatic Impairment on the Pharmacokinetics (PK) of Evobrutinib (M2951)

**Short Title:**

Effect of hepatic impairment on evobrutinib PK

**Rationale:**

The purpose of the study is to describe the evobrutinib pharmacokinetics (PK) in participants with different stages of hepatic impairment compared to a control group of participants with normal hepatic function. The results of this study will contribute to the understanding of the evobrutinib metabolism and inform recommendations on dose adjustments in participants with hepatic impairment.

**Objectives and Endpoints:**

| Objectives  | Endpoints   |
|---|---|
| Primary   |   |
| To investigate the PK of evobrutinib after a single dose to participants with hepatic impairment compared to participants with normal hepatic function                  | AUC 0-∞ , and C max   |
| Secondary   |   |
| To assess the safety and tolerability of evobrutinib when administered as a single dose to participants with normal hepatic function and with impaired hepatic function | Occurrence of treatment-emergent adverse events (TEAEs), changes from Baseline in laboratory safety tests, 12-lead electrocardiogram (ECG) morphology and time intervals (PR, QRS, RR, QT, and QTcF), and vital signs from time of first dose to the End of Study   |
| To characterize the effect of hepatic function on the PK of evobrutinib through secondary PK endpoints  | t max , t 1/2 , AUC 0-12 and AUC 0-24 , AUC 0-t , CL/f, V z /f, unbound fraction in plasma (f u ), AUC for unbound drug from time zero to infinity (AUC 0-∞,u ), unbound C max (C max,u ), and unbound apparent oral clearance (CL u /f) |

**Overall Design:**

This is an open-label, nonrandomized, parallel-group, single-center, single oral dose, Phase I study to investigate the PK and safety of evobrutinib in participants with different degrees of hepatic impairment compared to participants with normal hepatic function. Participants will be assigned to one of 3 groups: normal hepatic function (Group 1), mild hepatic impairment (Group 2), or moderate hepatic impairment (Group 3). Participants of Group 2 (8 participants with mild hepatic impairment) will be recruited in parallel with participants of Group 3 (8 participants with moderate hepatic impairment). After completion of enrollment of both Group 2 and Group 3, Group 1 consisting of 8 healthy participants will be recruited to match the group mean value to the participants of Group 2 and Group 3 regarding age ( $\pm 10$  years;  $\geq 18$  years old and  $\leq 79$  years old), and weight ( $\pm 10\%$ ;  $\geq 50$  kg and  $\leq 120$  kg). Efforts will also be made to have adequate sex representation in Group 1 (+ 2/- 2 male or female participants) that is similar to Groups 2 and 3. Up to 4 additional participants may be recruited in Group 1 for matching purpose.

**Disclosure Statement:**

This is an open-label, parallel group PK study with 3 arms.

**Number of Arms:** 3

**Blinding:** No blinding

**Number of Participants:**

A maximum of 28 participants will be assigned to study intervention such that approximately 24 to 28 evaluable participants complete the study. Each of the 3 groups is planned to include 8 participants. Up to 4 additional participants may be added into Group 1 for matching purpose. Based on the observed total variability of the primary PK endpoints for similar doses of evobrutinib in the most recent Phase I studies, the coefficient of variation (CV) of the geometric mean for AUC and  $C_{max}$  is expected to be between 30% and 60%.

[figure not shown]
**Study Intervention Groups and Duration:**

The duration of the study will be up to 33 days: Participants will be screened between Day -28 to Day -2, dosing will occur on Day 1, PK sampling and safety assessments will occur on Day 1 through to Day 2 and the Follow-Up visit between Day 4 and Day 6.

**Involvement of Special Committee(s):** No

## 1.2

### Schema

Abbreviations: PK= Pharmacokinetics

### 1.3 Schedule of Activities

| Assessments & Procedures                    | Screening
(Baseline
if Day -1
value not
available) | Study Day |   |   | Follow-Up/
Discontinuation | Notes   |
|---|--|-----------|---|---|-------------------------------|---|
| Study Day                                   | -28 to -2  | -1        | 1 | 2 | 4 to 6                        | Day -1 value will be used as baseline if available. For ECG and vital sign, Day 1 predose value will be used as baseline.   |
| Informed Consent                            | X  |           |   |   |                               | Prior to any screening activity   |
| Inclusion and Exclusion Criteria            | X  | X         |   |   |                               |   |
| Demography                                  | X  |           |   |   |                               |   |
| Hospitalization                             |  | X         | X | X |                               | Participants may be discharged 32 hours after administration of study intervention  |
| Full Physical Examination                   | X  | X         |   |   |                               |   |
| Medical History (includes substance usage)  | X  |           |   |   |                               | Substances: drugs, smoking history, alcohol intake, use of caffeine or xanthine-containing beverages  |
| Ultrasound and Assessment of Encephalopathy | X  |           |   |   |                               | For participants with hepatic impairment only   |
| Serum Pregnancy Test (WOCBP only)           | X  | X         |   |   | X                             |   |
| Drug and Alcohol Test                       | X  | X         |   |   |                               | See Appendix 5  |
| Clinical Laboratory Tests                   | X  | X         |   | X | X                             | See Appendix 5  |
| 12-lead ECG                                 | X  |           | X |   | X                             | Single ECG assessments will be conducted; Day 1: at predose (as baseline) and 1 hour postdose   |
| Vital Signs                                 | X  | X         | X | X | X                             | Includes height & weight collected at Screening only
Day 1: at predose (as baseline) and 1 hour postdose; Day 2 at 32 hours postdose.
See Section 8.2.2 . |
| CCI   |  |           |   |   |                               |   |

| Assessments & Procedures             | Screening
(Baseline
if Day -1
value not
available) | Study Day |   |   | Follow-Up/
Discontinuation | Notes   |
|--------------------------------------|--|-----------|---|---|-------------------------------|---|
| Study Day                            | -28 to -2  | -1        | 1 | 2 | 4 to 6                        | Day -1 value will be used as baseline if available. For ECG and vital sign, Day 1 predose value will be used as baseline. |
| Administration of Study Intervention |  |           | X |   |                               | Administration will occur 30 mins after starting a standard breakfast   |
| AE & SAE Review                      | X  | X         | X | X | X                             |   |
| Concomitant Medication Review        | X  | X         | X | X |                               |   |
| PK sampling                          |  |           | X | X |                               | Predose, 0.25, 0.5, 1.0, 1.5, 2.0, 3.0, 4.0, 6.0, 8.0, 10.0, 12.0, 16.0, 24.0, 32.0 hours postdose. See Section 8.5.      |
| PK sampling for free fraction        |  |           | X |   |                               | 1.5, 4, and 12 hours postdose. No separate blood collected. Backup samples will be used See Section 8.5                   |

Abbreviations: AE = Adverse event; ECG = Electrocardiogram; PK= Pharmacokinetics; SAE = Serious adverse event; WOCBP = woman of childbearing potential

## 2 Introduction

Evobrutinib is an oral, selective, irreversible inhibitor of Bruton's tyrosine kinase (BTK) which is in clinical development for the treatment of autoimmune diseases, e.g., multiple sclerosis (MS), rheumatoid arthritis (RA), and systemic lupus erythematosus (SLE).

Detailed information on the chemistry, pharmacology, efficacy, and safety of evobrutinib is in the current version of the Investigator's Brochure (IB).

### 2.1 Study Rationale

The purpose of the study is to describe the evobrutinib pharmacokinetics (PK) in participants with different stages of hepatic impairment compared to a control group of participants with normal hepatic function. The results of this study will contribute to the understanding of the evobrutinib metabolism and inform recommendations on dose adjustments in participants with hepatic impairment.

### 2.2 Background

Evobrutinib (also known as M2951 and MSC2364447C) is an oral, selective, irreversible inhibitor of BTK. Bruton's tyrosine kinase is a crucial intracellular kinase in the B cell antigen receptor (BCR) signaling pathway. The mode of action of evobrutinib and nonclinical data support clinical development in a broad spectrum of autoimmune and inflammatory disorders involving aberrant B cell and myeloid cell activity. Inhibition of BTK is expected to achieve profound B cell silencing. Thus, BTK inhibition could provide clinical benefit in the treatment of multiple autoimmune diseases including RA, SLE, and MS.

CCI

CCI

Additional details of the safety, efficacy, and PK of evobrutinib may be found in the current version of the IB.

## 2.3

### Benefit/Risk Assessment

As of July 31, 2019, approximately 1,214 adults have been exposed to evobrutinib including healthy participants, participants with relapsing multiple sclerosis (RMS), SLE, or RA, and participants with renal impairment. Evobrutinib was generally well tolerated in all participants. The treatment-emergent adverse events (TEAE)s have been primarily mild to moderate in severity.

The aim of the study is to describe PK of evobrutinib in participants with different stages of hepatic impairment compared to a healthy control group. The results of this study will contribute to the understanding of the evobrutinib metabolism and inform recommendations on dose adjustments in participants with hepatic impairment.

CCI

More detailed information about the known and expected benefits and risks and reasonably expected adverse events (AE)s of evobrutinib may be found in Section 4.2 and the IB.

Based on the available nonclinical and clinical data to date, the conduct of the study, as specified in this protocol, is considered justifiable.

## 2.3.1 Risk assessment

| Identified and Potential Risks of Clinical Significance       | Summary of Data/Rationale for Risk   | Mitigation Strategy   |
|---|--|---|
| Study Intervention(s) [evobrutinib]                    |  |   |
| Identified risks:

Elevated liver transaminases. | 
Elevated liver transaminases have been observed in patients treated with evobrutinib across the program and is considered an important identified risk (for details see current IB). Elevations of liver transaminases were frequent, generally mild (Grade 1), asymptomatic and reversible, and occurred within 6 months of treatment. However, more severe cases were reported. This has not been observed in healthy participants after a single dose nor in patients within a week of treatment with evobrutinib.
 | 
As a single low dose of evobrutinib will be administered in this study, and given the short half-life of evobrutinib, worsening of liver function is unlikely to occur. Study participants will be confined, and liver tests will be monitored during the study.
                                   |
| Potential risks:

Embryo-fetal toxicity          | 
Based on nonclinical findings, embryo-fetal toxicity is considered as an important potential risk in participants exposed to evobrutinib.
   | 
Female participants of childbearing potential must not be pregnant, must have a negative pregnancy test at the time of enrollment and use highly effective contraception (Section 5.1) during the study period and for 120 days after the last dose and agree not to donate eggs for reproduction.
 |

| Identified and Potential Risks of Clinical Significance | Summary of Data/Rationale for Risk  | Mitigation Strategy   |
|---|---|---|
| Study Procedures                                 |   |   |
| Blood draw  | Blood draws have the potential to cause discomfort and adverse events such as fainting or hematoma. | Amount of blood drawn will be strictly controlled. Participants will be in a hospital setting with support from highly trained professionals.           |
| Electrocardiogram (ECG)                                 | Contact allergies can develop during ECG procedures.  | Participants with known contact allergies will not be included in the study. During ECG participants will be monitored by highly trained professionals. |
| Other  |   |   |
| Not applicable.   |   |   |

### 2.3.2 Benefit Assessment

The aim of the study is to describe the PK of evobrutinib in participants with different stages of hepatic impairment compared to a healthy control group. The results of this study will contribute to the understanding of the evobrutinib metabolism and inform recommendations on dose adjustments in participants with hepatic impairment. Therefore, participants will contribute to the process of developing new therapies in areas of unmet need where evobrutinib could be used.

### 2.3.3 Overall Benefit: Risk Conclusion

The risk minimization proposed in this study includes a low dose of evobrutinib, single dosing and site admission of the study participant for the duration of the study to allow continuous safety monitoring. This clinical study will be conducted in compliance with the clinical study protocol, International Council for Harmonization and Good Clinical Practices (ICH GCP), and any additional applicable regulatory requirements.

Considering the potential risks and the measures taken to minimize risk to participants in this study, the conduct of the study is considered as justified in the participants with hepatic impairment.

### 3 Objectives and Endpoints

| Objectives  | Endpoints   |
|---|---|
| Primary   |   |
| To investigate the PK of evobrutinib after a single dose to participants with hepatic impairment compared to participants with normal hepatic function                  | AUC 0-∞ , and C max   |
| Secondary   |   |
| To assess the safety and tolerability of evobrutinib when administered as a single dose to participants with normal hepatic function and with impaired hepatic function | Occurrence of treatment-emergent adverse events (TEAEs), changes from Baseline in laboratory safety tests, 12-lead ECG morphology and time intervals (PR, QRS, RR, QT, and QTcF), and vital signs from time of first dose to the End of Study   |
| To characterize the effect of hepatic function on the PK of evobrutinib through secondary PK endpoints  | t max , t 1/2 , AUC 0-12 and AUC 0-24 , AUC 0-t , CL/f, V z /f, unbound fraction in plasma (f u ), AUC for unbound drug from time zero to infinity (AUC 0-∞,u ), unbound C max (C max,u ), and unbound apparent oral clearance (CL u /f) |
| Tertiary/Exploratory  |   |
| Not applicable.   |   |

### 4 Study Design

#### 4.1 Overall Design

This is an open-label, nonrandomized, parallel-group, single-center, single oral dose, Phase I study to investigate the PK and safety of evobrutinib in participants with different degrees of hepatic impairment compared to participants with normal hepatic function.

Participants with hepatic impairment will be assigned to a group of mild (Child-Pugh class A) or moderate (Child-Pugh class B) hepatic impairment at Screening by use of the Child-Pugh system ([Table 1](#) and [Table 2](#)) and, in addition to participants with normal hepatic function, assigned to one of the following groups:

- Group 1: normal hepatic function
- Group 2: mild hepatic impairment
- Group 3: moderate hepatic impairment

Participants of Group 2 (8 participants with mild hepatic impairment) will be recruited in parallel with participants of Group 3 (8 participants with moderate hepatic impairment). After completion

of enrollment of both Group 2 and Group 3, Group 1 consisting of 8 healthy participants will be recruited to match the group mean value to the participants of Group 2 and Group 3 regarding age ( $\pm 10$  years;  $\geq 18$  years old and  $\leq 79$  years old), and weight ( $\pm 10\%$ ;  $\geq 50$  kg and  $\leq 120$  kg). Efforts will also be made to have adequate sex representation in Group 1 (+2/-2 male or female participants) that is similar to Groups 2 and 3. Up to 4 additional participants may be recruited in Group 1 for matching purpose.

**Table 1** Child-Pugh Grades/Class of Hepatic Impairment

| Child-Pugh Score | Child-Pugh Grade/Class | Severity of Hepatic Impairment |
|------------------|------------------------|--------------------------------|
| 5-6              | A                      | Mild                           |
| 7-9              | B                      | Moderate                       |
| 10-15            | C                      | Severe a            |

a Participants with severe hepatic impairment will not be included in this study.

**Table 2** Child-Pugh Criteria (FDA – Guidance for Industry, 2003)

|                                   | Points Scored for Observed Findings |            |          |
|-----------------------------------|-------------------------------------|------------|----------|
|                                   | 1                                   | 2          | 3        |
| Encephalopathy grade a | none                                | 1 or 2     | 3 or 4   |
| Ascites b              | absent                              | slight     | moderate |
| Serum bilirubin (mg/dL)           | < 2                                 | 2 to 3     | > 3      |
| Serum albumin (g/dL)              | > 3.5                               | 2.8 to 3.5 | < 2.8    |
| Prothrombin time, sec prolonged   | < 4                                 | 4 to 6     | > 6      |

a Encephalopathy will be assessed by an experienced physician at Screening using the following criteria:

- Grade 0: normal consciousness, personality, neurological examination, electroencephalogram
- Grade 1: restless, sleep disturbed, irritable/agitated, tremor, impaired handwriting, 5 cycles per second waves
- Grade 2: lethargic, time-disoriented, inappropriate, asterixis, ataxia, slow triphasic waves
- Grade 3: somnolent, stuporous, place-disoriented, hyperactive reflexes, rigidity, slower waves
- Grade 4: unrousable coma, no personality/behavior, decerebrate, slow 2 to 3 cycles per second delta activity.

b Ascites will be assessed by an experienced physician by physical examination as well as ultrasound examination at Screening using the following criteria:

- Absent: No ascites is detectable by manual and also not by ultrasound investigation.
- Slight: Ascites palpitation doubtful, but ascites measurable by ultrasound investigation.
- Moderate: Ascites detectable by palpitation and by ultrasound investigation.

Grading of hepatic impairment with the Child-Pugh system, including ultrasound examination for detection and classification of ascites as well as assessment of hepatic encephalopathy, will only be performed on participants with hepatic impairment.

The duration of the study will be up to 33 days: Participants will be screened between Day -28 to Day -2, dosing will occur on Day 1, PK sampling and safety assessments will occur on Day 1 through to Day 2 and the Follow-Up visit between Day 4 and Day 6.

## 4.2

### Scientific Rationale for Study Design

A parallel design with a small number of participants with hepatic impairment and controls with normal hepatic function is the standard design for hepatic impairment studies, in line with the FDA and EMA guidance/guidelines (FDA Guidance for Industry 2003, EMA Guideline CPMP/EWP/2339/02 2005).

In a CYP3A4 drug-drug interaction (DDI) study with evobrutinib (study MS200527-0054, a Phase I, open-label, single-sequence, three-period trial to investigate the effect of CYP3A4 inhibitors on the PK of M2951 in 16 healthy participants), an approximately 3-fold decrease of clearance was observed in participants receiving evobrutinib concurrently with the moderate (fluconazole) and the strong (itraconazole) CYP3A4 inhibitor. Assuming similar magnitude of increase in half-life for evobrutinib in the moderate hepatic impairment group, the predicted half-life would be 6 hours (increased 3 folds from 2 hours under normal condition) for the moderate hepatic impairment group. Therefore, sampling until 32 hours is sufficient for this study. Since evobrutinib showed concentration independent protein binding in human plasma, limited samples will be taken for free fraction measurement at 1.5 hours (anticipated peak concentration) and 12 hours (anticipated trough concentration when given BID). Considering the PK profile of evobrutinib, free trough concentration at 12 hours (anticipated trough concentration when given BID) may not be measurable, therefore one additional sample will be taken at 4 hours in order to have measurable free concentration at lower concentration range. Since there is no pharmacologically active metabolite, metabolite PK profile will not be evaluated in this study.

## 4.3

### Justification for Dose

Evobrutinib exposure increased when given with either a high-fat or low-fat meal. Mean  $AUC_{0-\infty}$  and  $C_{max}$  following administration of the tablet formulation increased by 70% and 27%, respectively, following a high-fat meal, and 50% and 25%, respectively, following a low-fat meal. The oral dose of 30 mg evobrutinib 30 minutes after a standard meal in this study is expected to have an exposure similar to the exposure achieved at 50 mg dosed under fasted condition, which was the dose used in the moderate (fluconazole) CYP3A4 inhibitor group in the CYP3A4 DDI study. Based on published data (de Jong 2015, de Jong 2017, de Jong 2018) for ibrutinib (a similar BTK inhibitor), the effect of mild/moderate hepatic impairment on exposure (~4-fold higher AUC for mild hepatic impairment and ~10-fold higher AUC for moderate hepatic impairment) was similar to the effect of a moderate CYP3A4 inhibitor (6-fold higher AUC with voriconazole). Therefore, assuming a similar effect for evobrutinib, the CYP3A4 DDI study outcome can be used to predict the change of exposure in participants with impaired hepatic function for evobrutinib. Given the ~3-fold increase in evobrutinib exposure observed with concurrent administration of a moderate CYP3A4 inhibitor (fluconazole) (MS200527-0054), a similar fold increase in evobrutinib exposure is expected in the mild/moderate hepatic impairment groups. The dose of 30 mg under fed conditions is lower than the intended commercial dose (45 mg under fed conditions). It was selected for this study in consideration of the potential 3-fold increase of exposure in mild/moderate hepatic impairment participants to ensure evobrutinib exposure remains below the level observed at the highest single dose of 500 mg and the highest multiple dose of 200 mg under fasted conditions in the first in human study.

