Free (unbound) fraction will be calculated as free concentration/total concentration. For each participant, 3 samples will be analysed to determine a percent of free fraction (unbound) evobrutinib. The values from these samples, if measurable, will be used to calculate a mean free fraction, presented as percentage. The percentage free will be divided by 100% to calculate unbound PK parameters.

The parameters C_{max} , t_{last} , and t_{max} will be obtained directly from the concentration-time profiles. If C_{max} occurs at more than 1 timepoint, t_{max} will be assigned to the first occurrence of C_{max} .

Partial areas should be calculated using the nominal dosing interval. The actual dosing interval calculated from the CRF should not be used. However, actual times for partial AUC intervals may be used if the sample was taken within +/-10% of the protocol defined time, and the partial area would not be calculable using scheduled time.

The regression analysis should contain data from at least 3 different time points in the terminal phase consistent with the assessment of a straight line on the log-transformed scale. Phoenix WinNonlin “best fit” methodology will be used as standard. However, in some cases, further adjustment may be made by the pharmacokineticist, if warranted, after agreement with the Sponsor. The last quantifiable concentration should always be included in the regression analysis, while the concentration at t_{max} and any concentrations <LLOQ which occur after the last quantifiable data point should not be used.

If $\%AUC_{extra}>20\%$ and/or the coefficient of correlation (Rsq adj) of λ_z is <0.8 and/or the observation period over which the regression line is estimated is less than twofold the resulting $t_{1/2}$, the rate constants and all derived parameters (e.g. $t_{1/2}$, $AUC_{0-\infty}$, CL/f etc.) will be listed, flagged and included in the parameter outputs and may be excluded from the descriptive statistics. Any flags will be included in the study specific SDTM/ADaM and the exclusion of parameters agreed with the sponsor.

In the case that profiles have a measurable pre-dose concentration less than or equal to 5% of its C_{max} value, the participant’s data without any adjustments will be included in all PK measurements and calculations. If the pre-dose value is greater than 5% of the C_{max} , the participant will be dropped from all PK evaluations. However, this participant’s data will be flagged and reported.

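### Does using one 3-fold exposure rise for both mild and moderate impairment undermine the 200 mg ceiling in the dose justification?

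*Protocol*

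**What the plan says.** Protocol Section 4.3 (Justification for Dose) builds its case in four steps.

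- Food: AUC and Cmax "increased by 70% and 27%, respectively, following a high-fat meal, and 50% and 25%, respectively, following a low-fat meal", so 30 mg fed "is expected to have an exposure similar to the exposure achieved at 50 mg dosed under fasted condition".
- Analogue: for ibrutinib, hepatic impairment gave a "4-fold higher AUC for mild hepatic impairment and ~10-fold higher AUC for moderate hepatic impairment". The section treats this as similar to a 6-fold AUC rise with voriconazole.
- Transfer: evobrutinib rose about 3-fold with fluconazole, so "a similar fold increase in evobrutinib exposure is expected in the mild/moderate hepatic impairment groups".
- Ceiling: the dose was chosen so that exposure "remains below the level observed at the highest single dose of 500 mg and the highest multiple dose of 200 mg", both fasted, in the first-in-human study.

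Protocol Section 4.2 (Scientific Rationale for Study Design) draws on the same interaction study. It reports that "an approximately 3-fold decrease of clearance was observed in participants receiving evobrutinib concurrently with the moderate (fluconazole) and the strong (itraconazole) CYP3A4 inhibitor". Carrying that size of effect over to half-life, it concludes that "the predicted half-life would be 6 hours (increased 3 folds from 2 hours under normal condition) for the moderate hepatic impairment group".

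**The concern.** Four-fold and 10-fold lie on either side of 6-fold. Their geometric mean, √(4 × 10) = 6.3, matches the inhibitor effect, but neither group does alone: 4/6 = 0.67 for mild and 10/6 = 1.67 for moderate. The study recruits and compares the two groups separately. A reader who takes the analogue at face value would therefore expect more than 3-fold in Group 3, yet the section shows its margin only at 3-fold.

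At stake is a statement in the benefit-risk argument. If AUC in moderate impairment rose by 4-fold or more, the claim to stay below the 200 mg multiple-dose level would not be shown for that group. Section 2.3.1 lists raised transaminases as an identified risk and cites the single low dose as mitigation, so the point deserves a check.

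**Working it through.** **Inputs**, all from Protocol 4.3: 30 mg fed, taken as 50 mg fasted; food factors 1.5 to 1.7 (AUC) and 1.25 to 1.27 (Cmax); analogue rises of 4 (mild), 10 (moderate) and 6 (inhibitor); evobrutinib inhibitor effect 3; ceilings of 200 mg (multiple dose) and 500 mg (single dose), fasted. **Assumption:** exposure is proportional to dose. The exposures observed at 200 and 500 mg are not in the readable text.

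**1. The plan's own chain.** 30 × 1.5 = 45 mg and 30 × 1.7 = 51 mg, which agrees with the stated 50 mg. Times 3: 135, 150 and 153 mg-equivalent at 45, 50 and 51 mg. All lie below 200 and 500, so the section's arithmetic reproduces.

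**2. Fold rise at which AUC reaches each ceiling.**
- 200 mg: 200/51 = 3.9, 200/50 = 4.0, 200/45 = 4.4.
- 500 mg: 500/51 = 9.8, 500/50 = 10.0, 500/45 = 11.1.

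**3. What the analogue would give if its ratios were scaled.** The protocol states no rule. Three plausible ones:

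| Rule | Moderate | Mild | Moderate AUC at 45 / 50 / 51 mg | Moderate Cmax |
|---|---|---|---|---|
| Proportional | 3 × 10/6 = 5.0 | 3 × 4/6 = 2.0 | 225 / 250 / 255 | 188–191 |
| Excess over 1 | 1 + 2 × 9/5 = 4.6 | 1 + 2 × 3/5 = 2.2 | 207 / 230 / 235 | 173–175 |
| Log scale | 3^(ln 10/ln 6) = 4.1 | 3^(ln 4/ln 6) = 2.3 | 185 / 205 / 209 | 154–156 |

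Cmax starts from 30 × 1.25 = 37.5 and 30 × 1.27 = 38.1 mg-equivalent and reaches 200 at 200/38.1 = 5.2-fold. It is below 200 under all three rules. AUC runs from 185 to 255, on both sides of 200 and about half of 500 at most.

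**4. Rounding.** The inputs are given as approximate. Letting 3 vary over 2.75 to 3.25 and 10 over 9.5 to 10.5 moves the fold from 3.56 (log scale) to 5.69 (proportional). At 50 mg that is 3.56 × 50 = 178 to 5.69 × 50 = 285. The analogue figures therefore do not settle whether 200 is passed. At the top corner Cmax would also pass 200 (5.69 × 38.1 = 217).

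**5. Evobrutinib's own data.** AUC is dose divided by CL/F, so a 3-fold fall in clearance is a 3-fold rise in AUC. Section 4.2 reports about that fall with both the moderate and the strong inhibitor: stronger CYP3A4 inhibition did not produce a visibly larger effect. The same section applies a similar magnitude to the moderate impairment group by name.

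**6. Consequence for the analysis.** Suppose half-life scaled fully with a 5-fold rise, giving 2 × 5 = 10 h. With a mono-exponential tail, the share of AUC beyond 32 h is 2^(−32/10) = 10.9%, against 2^(−32/6) = 2.5% at 6 h. The SAP (16.1.4) flags extrapolation above 20%, which needs 32/log2(5) = 13.8 h, and flagged parameters "will be listed, flagged and included in the parameter outputs and may be excluded from the descriptive statistics". The sampling schedule serves across the whole range.

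**The case for a change.** The strongest case for a change is that the section says the dose was selected to ensure exposure below both ceilings, and it names the 200 mg one alongside the 500 mg one. None of the three scaling rules returns 3-fold for moderate impairment, all give at least 205 mg-equivalent at the protocol's own 50 mg, and the strong-inhibitor result is not invoked in Section 4.3. Nor would a plateau under CYP3A4 inhibition prove a plateau in cirrhosis, which can affect more than one route of elimination.

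Part of this stands. Calling 4-fold and 10-fold both similar to 6-fold is loose, and the readable text does not show the AUC margin against 200 mg above about 4-fold.

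The rest is weaker than it looks. Section 4.3 uses the analogue to argue that inhibitor data can stand in for impairment data, not as a calibration curve. As a calibrator the 10/6 ratio is poor: the inhibitor was voriconazole for one drug and fluconazole for the other, and by the titles in the reference list the analogue's inhibitor and impairment results come from different studies, one of the inhibitor studies in patients with B-cell malignancies. The crossing of 200 mg also depends on dose proportionality and on the regimen behind that multiple dose. If exposure rose more than in proportion to dose, or if the 200 mg level means daily exposure under divided dosing, 4- to 5-fold could still lie below it.

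**Conclusion.** The concern identifies loose reasoning, not an error that needs correcting. The stated chain reproduces at 135 to 153 mg-equivalent. The 4.1- to 5.0-fold values, and the 185 to 255 mg-equivalent range around 200 mg, are extrapolations that the protocol does not make, and they rest on dose-proportional exposure. The one evobrutinib-specific result in the readable text supports about 3-fold and sits in the adjacent section, drawn from the same study. For a single dose, the like-for-like ceiling is the 500 mg level, which holds up to about 10-fold; only carrying the analogue's 10-fold over unscaled (450 to 510 mg-equivalent) would reach it, and that ignores that evobrutinib's inhibitor effect was half the analogue's.

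Sections 4.2 and 4.3 can be reconciled by reading them together. A separate range for moderate impairment would rest on a choice of scaling rule that reasonable statisticians would dispute, and it would alter no sampling time, analysis or conclusion. The study exists to measure the fold rise in each group and reports it with 90% confidence intervals, so the forecast is replaced by data. This view would change if the observed exposures at 200 mg proved lower than dose proportionality implies. Nothing here judges the dose itself.
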